## **b. INNOVATION**

### **b.1. Improving Clinical Practice: Personalized Adaptive Interventions**

The proposed study is highly innovative in five ways. **First**, the service delivery approach being tested can lead to more children receiving effective trauma-focused treatment while reducing the overall burden of cost to the provider, patient, payer and society. **Second**, within-treatment changes will identify potential mechanisms of change within standard TF-CBT and Step One to produce practice-relevant information to refine treatment delivery within both treatments. **Third**, SC-TF-CBT utilizes a multi-method minimal therapist-assisted approach based on newer methods (i.e., parent-led treatment, internet and website support [e.g., information and video demonstration], telehealth, and converting a therapist EBP manual into a tool for patients) to deliver Step One, a novel first-line at-home parent-led treatment (see b.2.) contributing to improved access. In fact, our pilot data indicated that a substantial percentage of children (77.6%) responded to Step One. **Fourth**, behavioral and environmental first-stage treatment tailoring variables are being examined to create an adaptive intervention where children can be matched to the appropriate intensity level *prior* to starting treatment. We will use a randomized block design to ensure that the two treatment conditions are balanced in regard to the candidate first-stage tailoring variables (see c.4. and c.4.1.). **Fifth**, within SC-TF-CBT, we will be utilizing time-varying tailoring variables that were identified from our pilot work to identify patients who need to step up immediately during stage-one treatment, and patients who are early responders and do not need stage-two treatment, thus leading to more personalized care.

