## STUDY DESIGN AND SAMPLE SIZE

**c.4. Design/Randomization.** Participants (N=216, ages 4-12) are randomized and will receive SC-TF-CBT or TF-CBT in a 1:1 ratio within community-based agencies. To ensure the two treatment conditions are balanced in regard to candidate first-stage tailoring variables, a randomized block design will be used. Based on pilot results (see c.1.3.), we will divide our sample into four cells based on whether the child has internalizing T-scores > or ≤71 and whether s/he has a critical life events score > or ≤16. Each cell will have equal numbers of children assigned to SC-TF-CBT and TF-CBT. See “Other Attachment” for study timeline.

**c.4.1. Design Considerations. Why not conduct a Sequential Multiple Assignment Randomized Trial (SMART) to build the adaptive intervention?**[34, 89] **1)** The adaptive SC-TF-CBT has been developed [4-6] and is at the developmental stage of comparing it to the standard in the field (i.e., TF-CBT). Many of the questions that would have been examined in a SMART, such as effectiveness with different ages,[25, 90, 91] different types of traumas,[25, 63, 92] different components and different lengths,[26] and with and without medication[93] have consistently suggested that standard TF-CBT is the recommended treatment. **2)** Our pilot studies, designed to inform this R01 application, documented that a first-line parent-led approach is feasible and acceptable, identified an estimated number of Step One responders, demonstrated the clinical utility of the responder status criteria, and identified candidate first-stage tailoring variables and second stage time-varying tailoring variable. Thus, there is ample evidence for testing the confirmatory stage of an optimized adaptive intervention with a randomized clinical trial in community settings. **3)** In order to re-randomize after non-response there typically needs to be least 35% to 65% non-responders,[94] and our preliminary data after Step One indicate that 22% were non-responders. Once the first-stage tailoring variables are identified and children can be matched to appropriate treatment at baseline, we anticipate that the Step One non-response rate would be even less.

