### **c.8. Data Analysis**

**c.8.1. Overview.** As in the R34 study, [name] will design a customized web-based randomization, data entry and management system for this project. We will use Qualtrics, a widely used secure web-based software package to collect data. Therapist will also use Excel to enter de-identified fidelity and cost data. Data will be uploaded to Box. (see Protection of Human Subjects 5.1.1.a.). [name] will work closely with the PI on the development of the data management system and with the PI/ Co-Is in the data management/analysis of the psychological, physiological and cost-related data.

**c.8.2. General Analytic Plan.** Descriptive and graphical statistics will be used to summarize the data on all randomized patients and to confirm that there are no group or site differences ( $p < .10$ ) in baseline demographics and clinical characteristics. If, for example, site differences are detected, we will account for it by including site indicators as fixed effects in the model. Distributional assumptions will be checked and appropriate transformations or non-parametric methods will be applied as necessary. For Primary Aim 1, we will use methods that are based upon establishing equivalence or non-inferiority of outcomes across treatment arms. These methods are used classically to evaluate whether a new treatment or condition is not inferior to an existing treatment. In general, Generalized Linear Models (GLM) will be used throughout. These models account for deviation from normal assumption of the dependent variables and to control for baseline covariates including patients' demographics and corresponding child and parents assessment measures. For Primary Aim 2, GLM will be used to quantify the relation between the value of the tailoring variables and the propensity of not responding to Step One. For Primary Aim 3, latent difference score models (LDS) will be applied. We will mainly use SAS 9.3 and Mplus 7.1 for GLM and mediation analysis. For Primary Aim 4, a cost effectiveness analysis (CEA) will be performed. CEA measures the incremental cost per unit improvement in outcomes. In the absence of outcome differences, costs will be examined using GLM.

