### **c.8.3. Specific Analyses for the Individual Study Aims**

**Primary Aim 1:** For the primary and secondary hypotheses, one-sided tests for non-inferiority will be applied as our goal is to show that the performance of the children in SC-TF-CBT will demonstrate comparable improvements to children in standard TF-CBT. For this non-inferiority test, the null hypothesis is written as  $H_0: \mu_1 - \mu_2 > r^*$ , where  $\mu_1$  denotes the average improvement in standard TF-CBT and  $\mu_2$  denotes the average improvement among children in SC-TF-CBT, and  $r^*$  represents the clinically significant difference expressed as common standard deviation units. The test will be applied to child outcomes, acceptability/satisfaction levels and parent outcomes that will be measured at post-treatment and at 6- and 12-month follow-up respectively.

Rejection of the null hypothesis will indicate that treatment outcomes of SC-TF-CBT are comparable to those from standard TF-CBT. For child and parent outcomes only, we will further apply GLM with repeated measures to detect whether the two treatment groups perform differently at any one time point. We will also document the percentage of responders to Step One and numbers and reasons for trigger and switch.

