## Amendment to the analysis plan 2.11.2022

**Aim 1.** We applied linear mixed-effect models (LME; SAS Institute Inc, 2015) with repeated measures to detect whether the two treatments performed differently at post-, 6- and 12-month assessments. Instead of 5% alpha we used a more stringent 2.5% alpha (Piaggio et al, 2012) for the non-inferiority analysis with the .41 margin. For the non-inferiority margin for the PCL-5, the clinically significant change threshold is 10 points although adult PTSD trials have used -5 (Foa et al., 2019) to -10 (Mathersul et al., 2019) points. We used -8.8 as the margin which was based on an expert panel and prior studies with adults (Acierno et al., 2017). Due to attrition (27.87%) being higher than planned (15%) and enrollment (N = 183) lower than the planned enrollment (N = 216), the power analysis was based on the actual randomization of 183 participants (SC-TF-CBT=91; standard TF-CBT=92).

**Aim 2.** We used backward stepwise logistic regression with predictors with  $p < .01$ . Besides predictors in the unadjusted model, demographics including children gender, age and race were included in the partially adjusted

model. In addition, three child primary outcomes were added for the full adjusted model.

**Aim 3.** Instead of LDS we used Linear mixed-effect models (LME) with repeated measures were used to detect whether the potential mechanisms of change declined significantly over time and whether the rate of change differed by treatment group with standard TF-CBT coded as 0 and Step One responders coded as 1. Further, we tested mediation and moderated mediation. If moderated mediation was not found mediation was tested with two regression equations: the first equation included mediators regressed on treatment condition and outcome variables at baseline; the second equation included outcomes regressed on treatment condition, mediators, and outcome variables at baseline. If there was no evidence of significant mediation, linear regression model (OLS) was applied to test the linear estimates as predictors for both outcome (TSCYC-PTS and CSDS-P).

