Recruitment will occur at two community mental health clinics in Florida that specialize in mental health treatment for children who have experienced trauma: The Crisis Center of Tampa Bay (CCTB; Hillsborough County) and Pasco Kids First (PKF; Pasco and Hernando Counties). A back-up agency, Suncoast Center Inc (Pinellas County). Children’s Home Society Duval, Clay, Baker, Nassau, and St. John) USF St. Petersburg Family Study Center (Pinellas County) and Directions for Living (Pinellas County) will be involved if recruitment goals are not being met (see Other Attachment). The role of these sites will be to recruit patients, coordinate study procedures with the Project Coordinator, comply with all study procedures and Institutional Review Board (Ebert, #51) requirements, and provide study treatment. Parents/guardians who seek trauma-focused services at these two/three community centers and have children between the ages of 4 to 12 years will be informed about the study and if interested, participate in a brief phone screening prior to setting up an assessment. Consistent with our approved study protocol implemented for our NIMH R34 Stepped Care TF-CBT grant, data will be obtained on site at the community centers. These centers currently provide psychotherapy and comply with confidentiality procedures consistent with agency policies including being compliant with the Health Insurance Portability and Accountability Act (HIPAA). For the proposed study, participants and/or research staff (e.g., independent evaluator, graduate research assistant, therapists) will enter scale responses directly into Research Electronic Data Capture (Qualtrics™) software system. Qualtrics™ is a secure web application (the site is encrypted using SSL and is backed up nightly) designed to manage on-line surveys and databases for clinical trials. Data captured in Qualtrics™ can be easily exported in statistical packages such as Mplus, SAS and SPSS. USF is an institutional partner of Qualtrics™. Subjects will have access only to complete their own scales. Fidelity ratings will be entered into Excel by the study therapists which can be easily converted to SPSS. All computer-generated data will be maintained in password-protected computers. Any measures collected on paper such as the mechanism of change measures will be double data-entered into Qualtrics™ and paper documents will be stored in the PIs office in locked filing cabinets at USF. No patient names will be recorded on assessment information as each participant will be assigned a record number. A separate record linking the code numbers to participant identifiers will be kept in a locked file, completely separate from the data.

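### Randomisation was blocked on four cells, but no Aim 1 text puts those cells in the model that yields the non-inferiority limit (minor)

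*Combined protocol and SAP*

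**What the plan says.** **Design.** Section b.1 states: "We will use a randomized block design to ensure that the two treatment conditions are balanced in regard to the candidate first-stage tailoring variables". Section c.4 forms four cells from the internalizing T-score (cut at 71) and the critical life events score (cut at 16), and adds: "Each cell will have equal numbers of children assigned to SC-TF-CBT and TF-CBT". It also says that participants "are randomized and will receive SC-TF-CBT or TF-CBT in a 1:1 ratio within community-based agencies".

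**Analysis of Aim 1.** Three texts bear on the model:

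- Section c.8.2 names baseline covariates by class only: patients' "demographics and corresponding child and parents assessment measures". The list is introduced as inclusive, not exhaustive. Site is conditional on a baseline comparison at p < .10: "If, for example, site differences are detected, we will account for it by including site indicators as fixed effects in the model".
- Section c.8.3 sets a one-sided non-inferiority test with no covariates listed, then says of child and parent outcomes: "we will further apply GLM with repeated measures to detect whether the two treatment groups perform differently at any one time point".
- The amendment of 2.11.2022 replaces this for Aim 1: "We applied linear mixed-effect models (LME; SAS Institute Inc, 2015) with repeated measures to detect whether the two treatments performed differently" at post-treatment, 6 and 12 months. It sets alpha at 2.5% with the 0.41 margin and gives no fixed-effects list.

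The two block scores are named as model predictors only for Aim 2 in c.8.3, where the outcome is Step One response.

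**The concern.** When allocation is balanced within cells and the cells predict outcome, the difference between arms varies less from trial to trial than a model without the cells assumes. The reported standard error is then too large and the confidence interval too wide. Non-inferiority here turns on whether one confidence limit clears 0.41 SD, so the model behind that limit should reflect how children were randomised.

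Attrition adds a second issue. The amendment reports 27.87%, against 15% planned. One block factor is, by its description in c.6.2, a count of life events that could affect taking part in treatment, so it could be related to dropout. Once children are lost, balance within cells is no longer guaranteed, and a model without the cells loses the protection the blocking was meant to give.

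**Working it through.** **The plan's own figure first.** Section c.9 gives 80% power with 92 per arm, margin 0.41 SD and true difference 0. With SD = 1, SE = √(2/92) = 0.1474, and power at one-sided 2.5% is Φ(0.41/0.1474 − 1.96) = 79.4%. That matches the stated 80%, so the same set-up is used below.

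**Inputs.**

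- Margin 0.41 on the common SD (c.8.3, c.9); alpha 2.5%, taken as one-sided (amendment).
- n: 183 randomised (amendment); 0.2787 × 183 = 51, leaving 132. Assumed: these 51 have no outcome and are lost equally, giving 66 per arm. If all 183 contribute, n is about 91.5 per arm.
- r, the baseline-outcome correlation: 0.5 or 0, assumed.
- R², the share of residual variance explained by the cells: 0.02, 0.05 or 0.10, assumed. The documents link the cells to no Aim 1 outcome.

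**Case 1: balance within cells holds.**

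- SE without cells: SE0 = √(2/n) × √(1 − r²). At n = 66 and r = 0.5 this is 0.1741 × 0.8660 = 0.1508.
- SE with cells: SE1 = SE0 × √(1 − R²).
- One-sided error without cells: Φ(−1.96/√(1 − R²)).
- Power without cells: Φ((0.41/SE0 − 1.96)/√(1 − R²)); with cells: Φ(0.41/SE1 − 1.96).

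| R² | SE0/SE1 | Error without cells | Power, n = 66, r = 0.5 | Power, n = 66, r = 0 | Power, n = 91.5, r = 0.5 |
|---|---|---|---|---|---|
| 0.02 | 1.010 | 2.39% | 77.9 → 78.4 | 65.5 → 66.2 | 89.5 → 89.9 |
| 0.05 | 1.026 | 2.22% | 78.2 → 79.7 | 65.7 → 67.6 | 89.9 → 90.7 |
| 0.10 | 1.054 | 1.94% | 78.8 → 81.8 | 66.2 → 69.9 | 90.5 → 92.2 |

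In this case the error is conservative throughout.

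**Case 2: random dropout.** Simulation of 183 children blocked in four cells, using the pilot prevalences in c.1.2 (32.7% and 28%, taken as independent), then 27.87% lost at random. With the truth at the margin and no baseline covariate (20,000 runs), the error without cells is 2.4% (R² = 0.05) or 2.1% (0.10). With a baseline covariate at r = 0.5 (10,000 runs) it is 2.2% or 2.1%. Adding the cells also changes the point estimate. In the second set of runs the limit moved on average by 0.007 or 0.015 SD units towards non-inferiority, with a standard deviation across trials of 0.022 or 0.029. It moved against non-inferiority in 38% or 30% of trials.

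**Case 3: dropout that differs by cell and arm.** The documents give no such figures, so this is illustration only. Assumed loss: 40% of SC-TF-CBT children with either factor high, 16% of other SC-TF-CBT children, 27.87% of standard TF-CBT children; high cells do worse; r = 0.5. Across separate simulations the error without cells is 3.3% to 3.6% (R² = 0.05) and 3.6% to 4.1% (0.10), against about 2.2% to 2.4% with cells. The opposite dropout pattern would push the error the other way.

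**The case against.** **The cells may already be handled.** The covariate list in c.8.2 is open-ended and the amendment does not withdraw it. For the CBCL internalizing outcome, the corresponding baseline measure is itself a block score. This stands in part: the finding is that no Aim 1 text includes the cells, not that they were left out of the fit. If the baseline outcome was adjusted for, the remaining R² is probably smaller.

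**The size rests on an assumed R².** This stands. The only signal in the documents is the pilot result in c.1.2. It concerns Step One response, with cutoffs chosen by a classification tree to separate responders from non-responders, so it does not establish an association with the Aim 1 outcomes.

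**Three stronger readings are tempting and unsupported.**

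- A reader might infer that the non-inferiority result, on which the Aim 4 amendment relies, is unsafe. The documents give neither the limits nor dropout by cell and arm. Where balance holds, omission makes non-inferiority harder to declare.
- A reader might infer the reverse: that omission can only be conservative and could never matter. That requires balance to survive to analysis, which 27.87% attrition does not assure; cases 2 and 3 show the limit moving both ways and the error rising.
- A reader might infer that site belongs in the model unconditionally, because c.4 speaks of allocation within agencies. That phrase may only name the setting, and c.4 defines the blocks by the two scores alone. Section 5.1.1.a says "Recruitment will occur at two community mental health clinics in Florida", with four further agencies as back-ups. In simulation at 132 children, site terms unrelated to outcome cost about 0.3 points of power for two agencies and 1.3 to 1.7 points for six, which can cancel what the cells gain.

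**Conclusion.** The gap is real and minor: the design blocks on four cells, and no Aim 1 text carries them into the model. With balance intact and R² between 0.02 and 0.10, the effect is slight and conservative. With the reported attrition, its direction in this particular trial cannot be known from the documents. The size depends on the assumed R², on r, and on treating the 27.87% as missing outcomes split equally between arms; the amendment does not say when that attrition occurred. The calculations apply to a linear model such as the LME. There is no evidence that the reported conclusion is wrong.

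**What to change.** In the Aim 1 model that gives the non-inferiority limit, include the two block factors or the four-level cell as fixed effects, alongside the baseline outcome. Keep the 0.41 margin on the common SD defined in c.8.3, not on the smaller residual SD after adjustment. The two-factor form is reasonable: if the pilot prevalences hold and are independent, the cell with both scores high has only 0.327 × 0.28 × 132 = 12 children.

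The amendment describes completed analyses. If the cells were fitted, saying so closes the point. If they were omitted, report the cell-adjusted model as a sensitivity analysis labelled post hoc. Add site only if allocation was in fact balanced within agency.

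The cost is 2 degrees of freedom for the two factors or 3 for the four-level cell, and no new data. If the cells are unrelated to outcome, simulated power falls by about 0.1 point at most where balance holds, and by about 0.4 points (64.9% to 64.5%) with four-cell adjustment after random dropout and no baseline covariate.

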**c.5. Therapist Training.** Prior to recruitment, therapists will receive detailed training in both SC-TF-CBT and standard TF-CBT (e.g., CBT, trauma narratives, establishing hierarchies, treatment protocols). [name] will use audiotapes of SC-TF-CBT and standard TF-CBT sessions from the pilot study to train therapists. The therapists will participate in weekly clinical supervision with the PI, and quarterly and as needed clinical consultation with Drs. Cohen, [name], and [name] (see letters of support).

**c.5.1. Treatment Integrity.** Treatment integrity in both conditions will be vigorously monitored through the use

of therapy manuals and adherence checklists (c.6.7.) on-going supervision, and regular monitoring and rating of video or audio taped therapy sessions. Manualized treatment protocols have been designed in our pilot work to standardize treatment.

Given that treatment will be provided by community therapists who may not have experience with these treatments, and there may be turnover with new therapists starting mid trial, we think it is important for the integrity of the study to ensure that both treatments are provided as intended and that fidelity be monitored in real time as therapists begin providing treatment. For each study therapist, the project coordinator under the supervision of the PI will review the first case for each type of treatment (e.g., Step One, Step Two, standard TF-CBT). If the first patient ends treatment early, sessions from the next patient will be reviewed so that three sessions for Step One, 9 sessions for Step Two and 12 sessions for standard TF-CBT are reviewed for each therapist. The PI will provide feedback to the therapist if any fidelity ratings are not completely met. In cases where there might be adherence concerns the project coordinator, under the supervision of the PI will review additional cases.

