**Primary Aim 4:** CEA examines the relative value of SC-TF-CBT (versus standard TF-CBT). CEA is performed from a societal perspective, meaning the costs to the health care system and the patient/parents are included. Treatment costs include direct (e.g., cost of therapy session), indirect (e.g., travel costs, missed work), and opportunity costs (e.g., value of lost time; see c.1.5. & c.7.4. for cost measures). CEA often incorrectly omits the opportunity cost of patient/parent time spent on therapy, phone support, and at-home parent-child meetings. Non-study mental health service costs include inpatient, outpatient, and school-based services and will be priced using the Florida Medicaid fee schedule. Research-specific costs (e.g., screening, research consent) for patients and staff are excluded. GLM will be used to examine differential treatment costs for SC-TF-CBT and standard TF-CBT. GLM can account for the likely skewed distribution of costs, differences in child characteristics, and a potential lack of independence within treatment locations. Incremental cost effectiveness ratios (ICER) are computed as incremental costs divided by incremental changes in morbidity/outcomes (symptom reduction and change in impairment/functioning). A single outcome measure (e.g., Quality Adjusted Life Years) might be preferable, but no established parameters for estimating morbidity in young children with trauma exist. If outcomes differ significantly, a non-parametric bootstrap with replacement method is used to generate a joint distribution of differential costs and outcomes. If outcomes do not differ, cost-effectiveness is determined by comparing treatment costs. Mean and median ICER ratios are reported as well as 95% confidence

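### No therapist term is specified for the Aim 1 non-inferiority analysis although therapists deliver both treatments, so the limit can be miscalibrated, most seriously by being too tight

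*Combined protocol and SAP*

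**What the plan says.** Section c.5 (Therapist Training) states: "Prior to recruitment, therapists will receive detailed training in both SC-TF-CBT and standard TF-CBT". Section c.5.1 (Treatment Integrity) then has the project coordinator, for every study therapist, "review the first case for each type of treatment (e.g., Step One, Step Two, standard TF-CBT"), so that three sessions for Step One, "9 sessions for Step Two and 12 sessions for standard TF-CBT are reviewed for each therapist". Therapists are thus crossed with arm by design. The same section expects them to differ in experience and to change over time: "treatment will be provided by community therapists who may not have experience with these treatments, and there may be turnover".

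For Aim 1 the amendment says only: "We applied linear mixed-effect models (LME; SAS Institute Inc, 2015) with repeated measures to detect whether the two treatments performed differently". It sets one-sided alpha at 2.5% and keeps the 0.41 SD margin. Section c.8.2 provides site indicators as fixed effects, but only if baseline site differences are detected. The Aim 1 paragraph of c.8.3 names no clustering term. Section c.4 blocks randomisation on internalizing score and critical life events, not on therapist. Section c.9 claims 80% power with 92 per group and has no therapist component.

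The one place where the plan acknowledges dependence between children is the Aim 4 cost model in c.8.3, which allows for "a potential lack of independence within treatment locations". That refers to locations, not therapists.

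**The concern.** Children treated by the same therapist tend to have correlated outcomes. When therapists work in both arms, two components act in opposite directions. A therapist who does well or badly with everyone (the main effect) largely cancels from the arm difference. A model without a therapist term still leaves that variance in the error, so the interval is slightly too wide. A therapist who does better with one treatment than with the other (therapist-by-arm) does not cancel. That variance is shared by all of the therapist's children in an arm, and a model that treats those children as independent understates it.

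Therapist-by-arm variation is plausible here. Section c.3.1 gives Step One three one-hour sessions plus calls, against twelve 90-minute sessions of standard TF-CBT. The pilot in c.1.4 recorded 425 against 1,158 therapist minutes per patient. Therapist skill has more room to act in one arm than in the other.

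In a non-inferiority test, a standard error that is too small raises the chance of wrongly declaring non-inferiority above the nominal rate. Non-inferiority is the trial's central claim. The amendment also gives it as the reason for replacing the cost-effectiveness analysis with a cost comparison, so an error in it would carry into Aim 4.

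**Working it through.** **1. The plan's own power figure.** Inputs from c.9: 92 per arm, margin 0.41 SD, true difference 0, SD 1. The standard error is √(2/92) = 0.1474, and 0.41/0.1474 = 2.781.
- With z = 1.96, power = Φ(2.781 − 1.96) = 79.4%, which matches the stated 80%.
- With z = 1.645, power = 87.2%, which does not.

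The stated power therefore follows from independent children and z = 1.96. No therapist component is in it.

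**2. Inputs for the check.**
- From the amendment: 183 randomised and 27.87% attrition, so 183 × (1 − 0.2787) = 132 children. An equal split of n = 66 per arm is assumed.
- Assumed, because the documents give none of these: K therapists, each with m = 66/K analysed children in each arm; main-effect variance T = 0.05; therapist-by-arm variance A from 0 to 0.05; total variance 1.

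**3. Formulas, for one time point.** Let the residual be R = 1 − T − A.
- True variance of the arm difference: (2/n) × (R + mA)
- Variance used without therapist terms: about (2/n) × [R + (T + A)(1 − (m − 1)/(n − 1))]
- Actual one-sided error: 1 − Φ(1.96/√ratio), where ratio = true/used

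Because (m − 1)/(n − 1) is small, the limit is too tight roughly when (m − 1)A > T. If A = T, this needs more than about 2 children per therapist per arm.

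**4. Two cases in full.**
- K = 10, A = 0.025: m = 6.6, R = 0.925. True factor 0.925 + 6.6 × 0.025 = 1.090. Factor used 0.925 + 0.075 × (1 − 5.6/65) = 0.994. Ratio 1.10, error 3.1% (2.9% in a 40,000-run simulation). The 97.5% half-width should be 0.356 SD instead of 0.340.
- K = 6, A = 0.05: m = 11, R = 0.90. True factor 0.90 + 0.55 = 1.45. Factor used 0.90 + 0.10 × (1 − 10/65) = 0.985. Ratio 1.47, error 5.3%. The half-width should be 0.411 SD instead of 0.339.

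**5. Actual one-sided error (nominal 2.50%), T = 0.05, 66 per arm.**

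| Therapists (m per arm) | A = 0 | 0.005 | 0.01 | 0.025 | 0.05 |
|---|---|---|---|---|---|
| 6 (11.0) | 2.26% | 2.55% | 2.85% | 3.76% | 5.31% |
| 10 (6.6) | 2.24% | 2.40% | 2.56% | 3.07% | 3.92% |
| 15 (4.4) | 2.23% | 2.33% | 2.43% | 2.73% | 3.24% |
| 22 (3.0) | 2.23% | 2.28% | 2.34% | 2.51% | 2.81% |

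**6. Power at zero true difference, 66 per arm.** With independent children it is 65%. It falls to 62% (K = 10, A = 0.025), 57% (K = 10, A = 0.05) or 50% (K = 6, A = 0.05). A therapist-level analysis with K − 1 degrees of freedom lowers these further, to 52%, 48% and 35% in simulation.

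**The case against.** A reader might infer that the limit is too tight whenever therapists differ in how well they deliver one treatment relative to the other. The documents do not support that. The main effect left in the error pulls the other way, and several cells of the table lie below 2.5%.

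The inputs are also assumed. Two agencies, several back-up agencies (5.1.1.a) and the statement that "there may be turnover with new therapists starting mid trial" are compatible with many small caseloads, where the effect is smallest. That each therapist treats several children per arm is an inference from c.5.1. Manuals, weekly supervision, first-case review and the 90% adherence threshold (c.5, c.5.1, 5.1.1.c) are all meant to limit differences between therapists. All of this stands, and it is why the size is given only as a range.

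The calculation gives both arms the same therapist-by-arm variance, whereas the reason for expecting it lies mainly in the therapist-led arm. If therapist variance were confined to that arm, the design effect would be 1 + (m − 1)ρ/2. With 8 therapists (m = 8.25), ρ = 0.05 and no main effect, that is 1.18 and an error of 3.6%. Variance in both arms gives 1.36 and 4.7%. So the effect would be smaller but still present.

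The inflation also assumes that therapists stand for a wider population. If the claim concerned only the participating therapists, their differing arm effects would not be sampling error. The plan does not state this choice. Section a.6 aims at dissemination into community practice, which favours the wider reading.

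Finally, the random-effects structure is not written out, and the amendment does not say outright that the non-inferiority limit comes from the mixed model. The supportable statement is that no therapist term is specified in any Aim 1 analysis. The conditional site effects in c.8.2 deserve mention, but they do not address therapist-by-arm variance.

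**Conclusion.** The concern holds as one of calibration. Therapists are crossed with arm, no therapist term is specified for the primary test, and the power figure assumes independent children. Under the stated assumptions (66 per arm with equal caseloads in both arms, main-effect variance 0.05), therapist-by-arm variance of 0.025 to 0.05 and 6 to 15 therapists give an actual one-sided error of about 2.7% to 5.3%. The upper end is back at the 5% that the amendment replaced. With interaction variance of 0 to 0.005 the error is 2.2% to just over 2.5%, and the limit is about right or slightly too wide. Which case applies cannot be read from the documents.

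A reader might go further and infer that the non-inferiority result is wrong, or that its decision interval should now be replaced. Neither follows. The documents report no estimate or limit to re-judge. The amendment describes the analysis as already done, so changing the decision rule now would be a post hoc change to the primary test.

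**What to change.** Report the number of therapists and the number of analysed children per therapist in each arm. Add a sensitivity analysis of the Aim 1 model with random effects for therapist and therapist-by-arm and Kenward-Roger degrees of freedom. State whether the conclusion at the 0.41 SD margin still holds, and therefore whether the Aim 4 cost comparison is still justified. Say whether inference is to the participating therapists or to therapists more widely.

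The cost is a re-run and a few sentences. Section c.5.1 produces an adherence rating for every patient and therapist, so therapist identity should be recoverable. The drawback is precision. With few therapists the interval may be noticeably wider: with 7 degrees of freedom the multiplier alone rises from 1.96 to 2.36, about 21%. For that reason the new interval should be reported beside the existing decision interval, not in place of it.
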